22.4.3 Handling of missing values, censoring, and discontinuations

Ineligible subjects and subjects who cancel registration before receiving any therapy will not be included in the efficacy analyses. Patients who receive at least one dose of the experimental therapy will be included in the safety analysis.

22.5 Secondary Objectives

22.5.1 Key Secondary Objectives

1. Progression free survival using RECIST 1.1 as assessed by the investigator. Progression will be defined as time from start of study therapy to disease progression or death (whichever occurs first)
2. Safety using CTCAE version 4.03
3. Overall survival from start of study therapy to death (any cause)

22.5.2 Exploratory Objectives

1. Estimate the response rate and PFS in the specific mutation subsets of exon 18 G719X, exon 20 S7681, exon 21 L861Q or compound mutations

22.5.3 Statistical Analysis for Secondary Objectives

Patients who are not able to get radiographic assessment for all reasons will be considered disease progression at the time they discontinue protocol therapy for the PFS analysis. Patients who stop therapy for reasons other than disease progression will be followed for disease progression. Patients who have not experienced an event of interest by the time of analysis will be censored at the date they are last known to be alive and progression-free. Overall survival is defined as the time from start of study therapy to death from any cause, and patients who are alive at the time of analysis will be censored at the last date of contact. Time to event endpoints will be summarized using the method of Kaplan and Meier as well as by Cox regression in the presence of covariates. Potential co-variates including smoking history, mutation subtype, gender, and performance status.

An exploratory subset analysis will estimate the objective response rate, PFS and OS in the specific mutation subsets of exon 18 G719X, exon 20 S7681, exon 21 L861Q or compound mutations.

The evaluation of safety using the AE using NCI CTCAE version 4.03. All patients who receive at least one dose of study treatment will be included in the safety analysis.

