4.0 OBJECTIVES AND ENDPOINTS

Table 1

	Objective	Endpoint	Analysis
Primary	Objective response rate	Patients experiencing a confirmed partial or complete response using RECIST 1.1 (appendix 4)	See Section 22
Key Secondary	Progression-free survival	Time from starting study therapy until disease progression using RECIST 1.1 or death (whichever occurs first) (appendix 4)	See Section 22
Key Secondary	Safety	Common Terminology Criteria for Adverse Events (CTCAE) to assess adverse events	See Section 22
Key Secondary	Overall survival	Time from starting study therapy until death	See Section 22
Exploratory secondary	ORR and PFS in the specific mutation subsets of exon 18 G719X, exon 20 S7681, exon 21 L861Q or compound mutations	RECIST 1.1 (appendix 4)	See section 22

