8.4 Follow-up Period

1. After discontinuing study therapy patients will be followed for overall survival every 3 months by telephone or review of medical records until death or a maximum of 2 years. **Subsequent therapy and survival status will be documented.** If molecular testing performed (e.g. molecular testing of tumor biopsy or circulating tumor DNA) the results of the testing will be recorded if available. Patients who discontinue therapy for reasons other than disease progression will be followed for disease progression. The imaging schedule is at the discretion of the treating physician, but the recommended interval is every 6 to 12 weeks.

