9.1.3 Definition of Evaluable Subjects, On Study, and End of Study

All patients who receive a dose of the study medication (osimertinib) will be considered evaluable. Patients who withdraw consent before starting study medication, sign informed consent document and are subsequently found ineligible, or do not start study medication will not be considered evaluable. Patients who start study medication and do not have a radiographic assessment due to clinical progression will be considered as having disease progression. Patients who have progressive disease, unacceptable toxicity, or withdraw consent will be considered as coming off study and the date of the most recent clinic visit or imaging will be considered the end of the study.

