13.2 Follow-up Requirements for patients who discontinue therapy prior to disease progression

Patients who do not start study drug will not have any study follow-up requirements. Patients who discontinue therapy for reasons other than disease progression will be followed for disease progression every 6-12 weeks at the discretion of the treating physician until disease progression and once patient stop study therapy they will be followed for overall survival every 3 months by telephone or by review medical records for a maximum of 2 years.

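### The PFS rule in 22.5.3 turns any missing radiographic assessment into a progression on the day therapy stops, which is wider than the plan's own PFS definition and section 9.1.3

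*Combined protocol and SAP*

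**What the plan says.** Table 1 in section 4.0 gives the PFS endpoint as "Time from starting study therapy until disease progression using RECIST 1.1 or death (whichever occurs first". Section 22.5.1 agrees: "time from start of study therapy to disease progression or death (whichever occurs first". Stopping treatment is not an event in either place.

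Two sections then add imputed events. Section 9.1.3 is narrow: "Patients who start study medication and do not have a radiographic assessment due to clinical progression will be considered as having disease progression". It gives no date for that event. Section 22.5.3 is broad: "Patients who are not able to get radiographic assessment for all reasons will be considered disease progression at the time they discontinue protocol therapy". Nothing limits the reasons, and no sensitivity analysis is planned.

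The next sentences of 22.5.3 say "Patients who stop therapy for reasons other than disease progression will be followed for disease progression", and that patients without an event "will be censored at the date they are last known to be alive and progression-free". Section 13.2 repeats that such patients "will be followed for disease progression every 6-12 weeks at the discretion of the treating physician until disease progression". Appendix 4 classes deterioration without objective progression as symptomatic deterioration, and asks that objective progression still be sought after treatment ends.

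**The concern.** Where the scan is missing because the patient has clinically progressed, an event at the stop date is reasonable. The difficulty is the patient who stops for toxicity, withdrawal of consent or loss to follow-up, has not progressed, and is never scanned. For that patient 22.5.3 creates an event that the endpoint definition does not recognise. If the patient later dies, the event is dated at the stop and not at the death.

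The ORR rule in 22.4.2 uses similar wording, but there a missing scan only makes the patient a non-responder. For PFS it also creates an event and a date.

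Two things are left open: whether the rule requires that there be no scan at all after baseline, and whether a later scan or death date takes precedence over the stop date. Two analysts could code the same patient differently. PFS is a key secondary endpoint of a trial meant to judge whether a larger study is worthwhile. The censoring sentence does not contradict the rule, because it covers only patients without an event.

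**Working it through.** **1. The plan's own figures.** No sample size, power or event count is given for PFS. The design figures in 22.4.2 are for ORR (stop at 3 or fewer of 17; not worthy of further study at 10 or fewer of 37). Exact binomial sums reproduce type I error 0.0948, type II error 0.0967, early-stopping probability 0.5489 and expected N = 17 + (1 − 0.5489) × 20 = 26.0. PFS does not enter, so none of these changes.

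**2. Who is caught.** The analysis set is everyone with at least one dose (22.1). The first on-study CT is Cycle 3 Day 1 (Table 4, footnote 9). With 28-day cycles (9.1) that is day 2 × 28 + 1 = 57. Section 13.1 lists several exits without progression, and the timing of imaging after stopping is left to the treating physician (8.4, 13.2). So the case can arise.

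| Never-scanned patient | Table 1 and 22.5.1 | 9.1.3 | 22.5.3 |
|---|---|---|---|
| Stops with clinical progression | Event only at death | Progression, undated | Progression at stop |
| Stops without progression, still alive | No event | Not imputed | Progression at stop |
| Stops without progression, later dies | Event at death | Not imputed | Progression at stop |

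**3. Size if none of the k had progressed.** Assumptions: n = 37, exponential PFS with median m, all k stops before the first scan, and the k patients otherwise like the rest. Each imputed early event lowers the starting level of the later curve by 1/37 = 2.7 points, so

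- median = m × log2(2(37 − k)/37)
- S(6) = ((37 − k)/37) × 2^(−6/m)

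| k | Median, m = 10 | S(6), m = 10 | Median, m = 19.3 | S(6), m = 19.3 |
|---|---|---|---|---|
| 0 | 10.00 | 66.0% | 19.30 | 80.6% |
| 1 | 9.60 | 64.2% | 18.54 | 78.4% |
| 2 | 9.20 | 62.4% | 17.75 | 76.3% |
| 3 | 8.78 | 60.6% | 16.95 | 74.1% |

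The 10-month median is assumed. The 19.3 months is the first-line figure in section 2.3, from a different mutation population.

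**4. Bias when some had progressed.** With k = 3, m = 10 and j true progressors, the truth is ((37 − j)/37) × 66.0%, while the rule gives 60.6% each time.

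| j | Truth | Rule | Bias (points) |
|---|---|---|---|
| 0 | 66.0% | 60.6% | −5.4 |
| 1 | 64.2% | 60.6% | −3.6 |
| 2 | 62.4% | 60.6% | −1.8 |
| 3 | 60.6% | 60.6% | 0 |

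Simulation (5000 trials per case, stops uniform on 0.3 to 1.84 months, administrative censoring uniform on 24 to 48 months) agrees. For j = 0 the truth is 66.4%, the rule gives 60.6% and censoring at the stop gives 66.4%.

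**5. Against sampling error.** At m = 10 the simulated SD is 2.2 to 2.4 months for the median and 7.4 to 8.2 points for six-month PFS. The largest shifts, 1.2 months and 5.4 points, are below one SD. At m = 19.3 the asymptotic SE of the median is 19.3/(0.693 × √37) = 4.6 months, against a shift of 19.30 − 16.95 = 2.35.

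**6. Mutation subsets.** If enrolment followed the frequencies in 1.2 (6%, 1.5% and 3% of *EGFR* mutations, ignoring compound mutations), the S768I subset would be 37 × 1.5/10.5 = 5.3 patients. One false event among 5 moves that curve by about 20 points. This analysis is exploratory.

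**7. Which censoring date.** Section 8.4 has patients "followed for overall survival every 3 months by telephone or review of medical records until death or a maximum of 2 years", a contact that can show survival without showing disease status. Carrying three unscanned patients event-free to such contacts gives S(6) = (34 × 0.6598 + 3)/37 = 68.7%, above the true 66.0%. Censoring at day 1 gives 66.0% in the simulation.

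**The case against.** The rule is prespecified and parallels the ORR rule. It can only add or advance events, and in an open-label, investigator-assessed single-arm trial that is the cautious direction. It contains the 9.1.3 rule and does not contradict it. On the natural reading, patients who stop without progression are followed and scanned, and so leave the rule. Few remain: the 6.8% discontinuation for adverse events in the phase III T790M trial (section 2.4) would be 0.068 × 37 = 2.5 patients over the whole treatment period, and only those who stop before day 57 and are never scanned count. Withdrawals and losses add an unknown number, but k = 3 with none progressed looks like an upper case. If early stoppers do worse than the rest, the bias is smaller still. Censoring also has a failure of its own: if all three had progressed and this was not documented, six-month PFS reads about 66% against a true 60.6%, now in the drug's favour.

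Most of this stands as a limit on size, and the last point is a real cost of the change. It does not remove the mismatch. A broader rule that contains 9.1.3 still records events outside Table 1 and 22.5.1. The natural reading about later scans is not written down. Caution is a good reason to report the rule as a sensitivity analysis, but a main estimate should follow its own endpoint definition.

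**Conclusion.** The concern holds and is minor. As written, 22.5.3 counts events that the PFS definition does not recognise and that 9.1.3 would not impute. Any resulting bias lowers PFS. It is zero if no patient goes unscanned or if every such stop was true progression.

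Under the assumptions above, one to three falsely imputed patients cost about 0.4 to 1.2 months of a 10-month median and 1.8 to 5.4 points of six-month PFS. The documents do not give the number of such patients. PFS carries no hypothesis test, so ORR, N = 37 and the two-stage decision stand.

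**What to change.** In 22.5.3:

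- Count as PFS events RECIST 1.1 progression, death at its own date, and documented clinical progression without a scan, as in 9.1.3, with its date defined.
- Align Table 1 and 22.5.1 with this, and say how it relates to symptomatic deterioration in Appendix 4.
- State that the missing-assessment rule means no scan after baseline, on or off therapy, and that later scans and deaths take precedence over the stop date.
- Censor other never-scanned patients at the last visit at which the investigator documented no progression, or at day 1 if there is none. Do not use a telephone or records contact that shows survival only.
- Keep the present rule as a conservative sensitivity analysis.

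The cost is wording in three places and one extra analysis, with no change in sample size and no added visits. A dated judgement of no progression is not a listed assessment in Table 4; where the visit record does not show one, the day 1 fallback applies. The main estimate would be too favourable if unscanned patients had progressed without documentation. Dating a late death at the death date also credits progression-free time without scans. The retained sensitivity analysis gives the lower figure in both cases.

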The current standard first-line therapy is a platinum doublet for patients with stage 4 disease and uncommon *EGFR* mutations. Platinum and pemetrexed has an objective response rate (ORR) of approximately 30% and a median PFS 4 to 5 months in patients with an *EGFR* mutation.^{18,23} The standard second-line therapies are immunotherapy and docetaxel. A response rate of approximately 5-10% and median PFS of approximately 3 months are observed with docetaxel, and with immunotherapy a response rate of 20% is observed in the intent-to-treat patient population. The response rate is estimated to be lower in the *EGFR* mutant patient population.^{13-15,24} In subset analyses of phase 3 trials of immunotherapy compared to docetaxel a survival benefit was not observed with immunotherapy in the *EGFR* mutation subset.¹³⁻¹⁵ A higher mutational burden and a history of smoking is associated with benefit from immunotherapy, and patients with *EGFR* mutant NSCLC have lower mutational burden and frequently a history of never smoking or light smoking.²⁵ These clinical and biomarker data have raised questions about the activity of immunotherapy in patients with *EGFR* mutant NSCLC.

Recently the second and third-line approval of erlotinib was rescinded by the FDA. Afatinib is approved in the second-line setting only for squamous histology NSCLC. This limits the availability of EGFR TKIs in the second-line setting for patients with *EGFR* mutations besides the exon 19 deletions and exon 21 L858R mutation. Thus, there are limited effective options for patients with uncommon *EGFR* mutations.

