5.2 Exclusion Criteria

Patients will be excluded from the study if they meet **any** of the following criteria:

1. Prior therapy with EGFR TKI therapy
2. Greater than 2 lines of prior systemic therapy for metastatic non-small cell lung cancer.
3. Any cytotoxic chemotherapy or other anticancer drugs from previous treatment regimen or clinical study within 14 days of first dose of study drug.
4. Treatment with an investigational drug within 5 half-lives of the compound
5. Other active malignancy \leq 2 years prior to study enrollment. EXCEPTIONS: Non-melanotic skin cancer or carcinoma-in-situ of the cervix. NOTE: If there is a history of prior malignancy, patients must **not** be receiving other specific treatment (i.e. hormonal therapy) for their cancer
6. Prior radiotherapy \leq 14 days
7. Untreated symptomatic brain metastases (treated brain metastases are allowed provided $>$ 14 days have elapsed from completion of radiotherapy and patient is neurologically stable as assessed by treating physician).
8. Malabsorption syndrome, refractory nausea and vomiting, chronic gastrointestinal diseases, inability to swallow the formulated product or previous significant bowel resection that would preclude adequate absorption of osimertinib
9. Detection of concurrent *EGFR* mutation with exon 20 T790M, exon 19 deletion, exon 21 L858R mutation or exon 20 insertion. Patients with compound (also referred to as multiple mutations) will be excluded if the molecular testing includes one of these mutations
10. Active pregnancy or breast-feeding: Pregnant women are excluded from this study because the effects of osimertinib on the development of the fetus are unknown, and there is potential for teratogenic or abortifacient effects. Because there is an unknown but potential risk for adverse events in nursing infants secondary to treatment of the mother with osimertinib, breastfeeding should be discontinued if the mother is treated with these agents.
11. Grade \geq 2 blurred vision, conjunctivitis, corneal ulcer, dry eye, or keratitis
12. Men who intend to father children during the study or within 4 months afterward are excluded
13. Major surgery within 4 weeks of first dose of study drug.

14. Any unresolved toxicities from prior therapy greater than CTCAE grade 1 at the time of starting study treatment, with the exception of alopecia or neuropathy

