7.1 Registration for Outside Sites

All patients signing informed consent at outside sites must be registered with Duke (including screen failures- indicate screen failure status on last page of eligibility checklist). The following documents are to be completed by the investigator and/or designee and faxed to [contact] or scanned/mailed to the Thoracic Oncology Protocol Office ([contact]): All supporting documents should be sent de-identified.

- TOP 1703 Eligibility Checklist with supporting source documents
- Signed Informed Consent

8.0 STUDY PERIODS (Visit Requirements):

The Schedule of Events (Table 4) summarizes the trial procedures to be performed at each visit. Individual trial procedures are described in detail below. It may be necessary to perform these procedures at unscheduled time points if deemed clinically necessary by the investigator.

For the purpose of scheduling evaluations and to allow for patient and investigator schedules, holidays and weather or other emergencies requiring clinical facilities to be closed, a window of 7 days will be applied to all study visits unless otherwise noted.

Furthermore, additional evaluations/testing may be deemed necessary by the Sponsor and or AstraZeneca for reasons related to subject safety.

TABLE 4: Schedule of Events

Assessment	Screening ¹ Days -28 to 0	D1 of every Cycle ^{1,2,13}	End of Study Treatment (EOT) ³	Follow-up ^{2,4,9}
Informed consent	X			
Inclusion/exclusion Criteria	X			
Demography Baseline Characteristics, Smoking Hx	X			
Medical History⁵	X	X	X	
Prior NSCLC therapies	X			
Physical exam & vital signs⁵	X	X	X	
Height	X			
ECOG Performance Status	X	X	X	
CBC with differential⁶	X	X	X	
Serum Chemistries⁷	X	X	X	
Serum pregnancy test⁸	X	X		
CT scan chest/abdomen⁹	X	X ⁹		
Brain MRI⁹	X	X ⁹		
Echocardiogram /MUGA¹²	X			
EKG¹⁰	X			
Tumor Histology	X			
EGFR mutation status	X			
Adverse event assessment	X	X	X	
Study drug and diary¹¹		Provide & Review	X	
Concomitant Meds	X	X	X	
Subsequent Therapy and Survival Status				X

¹Within 28 days prior to Day 1 of study therapy unless otherwise noted. If screening (baseline) hematology and serum chemistries performed within 14 days of D1 of cycle 1, these do not need to be repeated.

² Unless otherwise noted, a window of 7 days will be applied to all study visits.

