22.2 Patient Demographics and Other Baseline Characteristics

Standard demographic information (age, gender, etc.) and prior therapies, smoking history and specific mutation type will be collected.

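### Does the secondary analysis need a pre-specified breakdown by prior line of therapy?

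*Combined protocol and SAP*

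**What the plan says.** Section 5.2 excludes only patients with "Greater than 2 lines of prior systemic therapy for metastatic non-small cell lung cancer", so 0, 1 or 2 prior lines are eligible. No share by line is planned or capped.

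Section 2.1 (Current therapy) gives different background figures by setting. For the first-line platinum doublet: "Platinum and pemetrexed has an objective response rate (ORR) of approximately 30% and a median PFS 4 to 5 months". For second-line chemotherapy: "A response rate of approximately 5-10% and median PFS of approximately 3 months are observed with docetaxel". Second-line immunotherapy is put at 20% in unselected patients, and the authors expect less than that in EGFR-mutant disease.

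Section 22.4.2 tests one null, ORR at most 20%, against ORR at least 40%, for all treated patients together.

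Section 22.5.3 summarises time-to-event endpoints by Kaplan-Meier and by Cox regression. On covariates it says: "Potential co-variates including smoking history, mutation subtype, gender, and performance status". On subsets: "An exploratory subset analysis will estimate the objective response rate, PFS and OS in the specific mutation subsets", these being G719X, S768I, L861Q and compound mutations. Prior line is named in neither place.

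The data exist. Section 22.2 states that "prior therapies, smoking history and specific mutation type will be collected", and Table 4 (Schedule of Events) has a screening row "Prior NSCLC therapies".

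**The concern.** The trial is meant to show whether a larger prospective study should follow (Section 1.1). Such a study would have to choose a line of therapy and a comparator, and Section 2.1 describes different standards by line. Mutation subsets do not show whether responses came from untreated patients, pretreated patients or both.

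The smallest positive result, 11 of 37 (29.7%), lies at the platinum-doublet figure and well above the docetaxel figure. What it means against Section 2.1 would depend on a line mix that is unknown in advance. A split by line chosen after seeing the data would be post hoc, whereas adding it now would take two sentences and no new data.

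**Working it through.** **1. The plan's own figures.** Inputs from Section 22.4.2: stop if 3 or fewer responders in 17; positive if 11 or more in 37. With X1 ~ Bin(17, p) and X2 ~ Bin(20, p):

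- Early stopping: P(X1 ≤ 3 | p = 0.20) = 0.5489.
- Type I error: Σ over x ≥ 4 of P(X1 = x)·P(X2 ≥ 11 − x) at p = 0.20 = 0.0948.
- Type II error: 1 − the same sum at p = 0.40 = 1 − 0.9033 = 0.0967.
- Expected N under the null: 17 + 20 × (1 − 0.5489) = 26.0.

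All four agree with the protocol. None depends on the line mix, because the null is a fixed number for the pooled population.

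**2. How much the mix could matter.** Assume a first-line reference of 30% and a pretreated reference of 10% (upper docetaxel figure), with an assumed first-line share w. Reference ORR = 0.30w + 0.10(1 − w). Probability of a positive trial if the drug only matched that reference:

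| w | Reference ORR | P(positive) |
|---|---|---|
| 0 | 10% | 0.001 |
| 0.25 | 15% | 0.015 |
| 0.50 | 20% | 0.095 |
| 0.75 | 25% | 0.285 |
| 1 | 30% | 0.540 |

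This is why the point looks serious. It rests, however, on treating 30% as a first-line value.

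**3. Is 30% a first-line value?** Section 2.1 cites references 18 and 23 for it. Reference 18 is AURA3; Section 2.3 describes its patients as having progressed on or after an EGFR TKI and reports 31.4% ORR and 4.4 months median PFS with chemotherapy. The title of reference 23 places it after progression on first-line gefitinib. This trial excludes any prior EGFR TKI. Section 1.2 also names pembrolizumab, alone or with chemotherapy, as standard first-line therapy and gives no response rate for it. The documents therefore hold no clean first-line benchmark, and the table in step 2 is only indicative.

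**4. When the mix stops mattering.** Exact (Clopper-Pearson, single-stage) 95% intervals for the pooled ORR: 11/37, 15.9–47.0%; 15/37, 24.8–57.9%; 17/37, 29.5–63.1%; 18/37, 31.9–65.6%. From 18/37 (48.6%) upward the lower limit exceeds 30%, the highest Section 2.1 figure, whatever the mix.

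**5. What a split would show.** Take 15/37 and assume 18 untreated and 19 pretreated patients:

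- Split A: 10/18 = 55.6% (30.8–78.5) and 5/19 = 26.3% (9.1–51.2). Fisher p = 0.099.
- Split B: 7/18 = 38.9% (17.3–64.3) and 8/19 = 42.1% (20.3–66.5). Fisher p = 1.0.

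The point estimates tell different stories, but in each split the two intervals overlap widely. If both lines share one response rate, then given 15/37 the hypergeometric probability is 0.26 for 7/18 and 0.05 for 10/18.

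At a true ORR of 40%, the chance that the lower limit exceeds its reference is 0.84 for 19 pretreated patients against 10% (6 or more responders needed), but 0.13 for 18 untreated patients against 30% (10 or more needed).

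**6. The Cox model.** With binary smoking and performance status, the named terms use 1 + 3 + 1 + 1 = 6 parameters. If all 37 patients had a PFS event, that is 37/6 = 6.2 events per parameter, falling to 37/7 = 5.3 with prior line added. Censoring or a stage 1 stop would lower both. Adding prior line here would do nothing for ORR.

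**The case for a change.** The strongest case for acting is that the split costs almost nothing and that naming it in advance is what gives it weight. Imprecision did not stop the authors from planning mutation subsets, some of which are likely to be smaller than a group by line. Below 18/37 the pooled result does not clear every background figure. Above it, the pooled result still does not say in which line activity was seen. For pretreated patients the split would be informative, as the 0.84 shows.

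Much of this stands as a statement about usefulness. The text does omit prior line, the background figures do differ by setting, and a breakdown made later would not be pre-specified. But it does not follow that results cannot be read by line: prior therapies are recorded, and the words potential and including leave the covariate list open. Nor does the protocol promise the comparison that the omission is said to block. Pre-specification also counts for less here than in a confirmatory setting, since the split would be descriptive, alongside mutation subsets already labelled exploratory, and would leave the decision rule alone.

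**Conclusion.** No change is needed. The omission is real but is a gap that analysts can fill sensibly: run exactly as written, the test against the 20% null keeps its stated error rates, and the Kaplan-Meier summaries remain valid for the population enrolled. No sample size, error rate or go/no-go conclusion moves. What is forgone is a pre-specified descriptive table. With about 18 patients per group it could help mainly for pretreated patients, and for untreated patients it would lack a sound comparator in these documents.

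The conclusion rests on three things: prior therapies being recorded well enough to count lines (which applying the Section 5.2 exclusion already requires), the line mix being reported with the baseline data, and an assumed near-even split for the precision figures. A more uneven mix would leave the smaller group less precise still. Authors who wish to report ORR with exact intervals and Kaplan-Meier curves for 0 versus 1–2 prior lines may do so, labelled exploratory, under the present wording.
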